### 10.4. Criteria for Potentially Clinically Significant Values (PCSV)

Table 20: Criteria for Potentially Clinically Significant Values (PCSV)

Parameter	PCSV	Comments
Clinical chemistry	y	
ALT	By distribution analysis:	
	>2 ULN and baseline ≤ 2 ULN	
	>3 ULN and baseline ≤ 3 ULN	
	>5 ULN and baseline ≤ 5 ULN	
	>10 ULN and baseline ≤ 10 ULN	
	>20 ULN and baseline ≤ 20 ULN	
AST	By distribution analysis:	
	>2 ULN and baseline ≤ 2 ULN	
	>3 ULN and baseline ≤ 3 ULN	
	>5 ULN and baseline ≤ 5 ULN	
	>10 ULN and baseline ≤ 10 ULN	
	>20 ULN and baseline ≤ 20 ULN	
Alkaline Phosphatase	> 1.5 ULN and baseline ≤ 1.5 ULN	
Total Bilirubin	> 1.5 ULN and baseline ≤ 1.5 ULN	
	> 2 ULN and baseline ≤ 2 ULN	
ALT and Total Bilirubin	ALT > 3 ULN and Total Bilirubin > 2 ULN and baseline ALT≤3 ULN or Total bilirubin ≤ 2 ULN	

Protocol: R4461-PLD-20100

Parameter	PCSV	Comments
СРК	> 3 ULN and ≤ 5 ULN and baseline ≤ 3ULN > 5 ULN and ≤ 10 ULN and baseline ≤ 5	
	ULN >10 ULN and baseline ≤ 10 ULN	
Creatinine	≥ 30% increase from baseline ≥ 60% increase from baseline	
Creatinine Clearance	≥15 - <30 (severe decrease in GFR) ≥30 - <60 (moderate decrease in GFR) ≥60 - <90 (mild decrease in GFR)	
Uric Acid Hyperuricemia	>408 μmol/L	
Blood Urea Nitrogen	≥17 mmol/L	
Chloride Hypochloremia: Hyperchloremia:	<80 mmol/L >115 mmol/L	
Sodium	$\leq$ 129 mmol/L $\geq$ 150 mmol/L	Must also be outside the normal range.
Potassium	< 3 mmol/L ≥ 5.5 mmol/L	Must also be outside the normal range.
Total Cholesterol	≥6.20 mmol/L (Under 18 yrs) >7.74 mmol/L (18 yrs +)	Must also be outside the normal range.
Triglycerides	<pre></pre>	Must also be outside the normal range.
Glucose	Hypoglycemia <3.9 mmol/L or 70 mg/dL  Hyperglycemia Fasting glucose ≥250 mg/dL or 13.9mmol/L and Increase in fasting glucose >50 mg/dL or 2.8mmol/L above baseline	Must also be outside the normal range.

Parameter	PCSV	Comments
		Comments
HbA1c	HbA1c ≥10.5% AND increase in HbA1c of ≥1.5% from baseline value	
Albumin	≤25 g/L	
Hematology		
WBC	< 3.0 Giga/L (3000/mm3)	Must also be outside the normal
	≥ 16.0 Giga/L (18 yrs +)	range.
Lymphocytes	>4.0 Giga/L	
	<0.6 Giga/L	
Neutrophils	< 1.5 Giga/L (1,500/mm3)	Must also be outside the normal range.
Eosinophils	> 0.5 Giga/L (500/ mm 3 )	
Losmopinis	or > ULN if ULN ≥ 0.5 Giga/L	
Monocytes	>1.5 Giga/L	
Hemoglobin	≤115 g/L (Male 18 yrs +)	Must also be outside the normal
	≤95 g/L (Female 18 yrs +)	range.
	≥185 g/L (Male 18 yrs +) ≥165 g/L (Female 18 yrs +)	

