8.4.2.1. Reasons for Permanent Discontinuation of Study Drug

Study drug dosing will be permanently stopped in the event of:

- Confirmation of pregnancy as evidenced by a positive serum pregnancy test
- Serious or severe allergic reactions considered related to study drug
- Severe liver injury or dysfunction for which no other reason can be found to explain, such as viral hepatitis A, B, or C; preexisting or acute liver disease; or another drug capable of causing the observed injury. Liver injury is defined as follows:
- For individuals with normal baseline transaminase and liver enzyme levels:
 - Alanine aminotransferase (ALT) or aspartate aminotransferase (AST) >8X upper limit of normal (ULN) or
 - ALT or AST >5X ULN on consecutive visits at least 2 weeks apart or
 - ALT or AST >3X ULN and total bilirubin >2X ULN (or international normalized ratio [INR] >1.5)
- For individuals with abnormal baseline transaminase and liver enzyme levels:
 - ALT or AST >3X over baseline and total bilirubin >2X over baseline (or INR >1.5)

- Patient withdraws consent
- Investigator's clinical judgment that it is in the best interest of the patient

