10. SAFETY EVALUATION AND REPORTING

10.1. Recording and Reporting Adverse Events

10.1.1. General Guidelines

The investigator must promptly record all AEs occurring during the study data collection, from the time of signing the informed consent form (ICF) to the end of the study (see Section 11.4.5.1). Medical conditions that existed or were diagnosed prior to the signing of the Informed Consent will be recorded as part of medical history. Abnormal laboratory values and vital signs observed at the time of Informed Consent should also be recorded as medical history. Any subsequent worsening (ie, any clinically significant change in frequency and/or intensity) of a pre-existing condition that is temporally associated with the use of the study drug should also be recorded as an AE.

At each visit, the investigator will determine whether any AEs have occurred by evaluating the patient. Adverse events may be directly observed, reported spontaneously by the patient, or by questioning the patient at each study visit. Patients should be questioned in a general way, without asking about the occurrence of any specific symptoms. The Investigator must assess all AEs to determine seriousness, severity, and causality, in accordance with the definitions in Section 10.2. The Investigator's assessment must be clearly documented in the site's source documentation with the Investigator's signature. The Investigator should follow up on serious adverse events (SAEs) (and AESIs) until they have resolved or are considered clinically stable; AEs should be followed until they are resolved or last study visit, whichever comes first.

Always report the diagnosis as the AE or SAE term. When a diagnosis is unavailable, report the primary sign or symptom as the AE or SAE term with additional details included in the narrative until the diagnosis becomes available. If the signs and symptoms are distinct and do not suggest a common diagnosis, report them as individual entries of AE or SAE.

Laboratory results, vital signs, and other diagnostic results or findings should be appraised by the Investigator to determine their clinical significance. Isolated abnormal laboratory results, vital sign findings, or other diagnostic findings (ie, not part of a reported diagnosis) should be reported as AEs if they are symptomatic, lead to study drug discontinuation, dose reduction, require corrective treatment, or constitute an AE in the investigator's clinical judgment.

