11.4.5.2. Other Safety

Vital Signs

Vital signs (temperature, pulse, blood pressure, and respiration rate) will be summarized by baseline and change from baseline to each scheduled assessment time with descriptive statistics.

Laboratory Tests

Laboratory test results will be summarized by baseline and change from baseline to each scheduled assessment time with descriptive statistics.

Number and percentage of patients with a potentially clinically significant value (PCSV) at any post-randomization time point will be summarized for each clinical laboratory test for all patients and separately for patients in whom the PCSV criterion was normal or missing at baseline.

Shift tables based on baseline normal/abnormal and other tabular and graphical methods may be used to present the results for laboratory tests of interest.

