#### 1.2.4. Modifications from the Statistical Section in the Final Protocol

The content of this SAP reflects the content of the statistical section of Protocol R4461-PLD-20100 Amendment 1 with the following exceptions:

- Protocol Section 4. Endpoints: The definitions of endpoints are clarified in SAP Section 5.7 by replacing:
  - "elevated baseline fasting TG" into "screening TG"
  - "elevated baseline HbA1c" for defining subgroup into "screening HbA1c" to match HbA1c strata (screening HbA1c ≤7.0%, >7.0%)
  - "baseline leptin" for defining Cohort into "screening leptin"
- Protocol Section 11.3.2. Safety Analysis Set: Safety analysis set (SAF) is replaced with DB SAF and SB SAF as follows in SAP Section 3.2:
  - DB SAF includes all randomized patients who received any double-blind study drug.
  - SB SAF includes all the patients in the double-blind SAF who also received at least 1 study drug in the single-blind treatment period.
- Protocol Section 11.4.5.4. Treatment Compliance: Compliance % calculation is replaced with study treatment administration interval compliance in SAP Section 5.8.8.
- Protocol Section 11.4.3. Efficacy Analyses: The randomization strata per IVRS in the analysis models (eg, MMRM) are replaced with actual strata in SAP Section 5.7 to reflect the actual disease characteristic for statistical modeling.
- Protocol Section 11.4.3. Efficacy Analyses: Due to the early termination of the study and subsequent limited number of participants enrolled, only descriptive summaries

Protocol: R4461-PLD-20100

and line plots for fasting TG, HbA1c, fasting glucose, liver fat (MRI-PDFF), and Daily Lipodystrophy Hunger Questionnaire (DLHQ) over time will be provided by treatment group. Spaghetti plots for fasting TG, HbA1c, fasting glucose, liver fat (MRI-PDFF), and DLHQ will be provided for individual patient data across visits for the endpoints by treatment group if applicable.

Protocol: R4461-PLD-20100

Date: May 16, 2024

• SAP Section 7 Timing of Statistical Analyses: First Step Analysis and Second Step Analysis will not be performed.

# 1.2.5. Revision History for Statistical Analysis Plan Version 1

This is the original version of the SAP.

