#### General common rules

All safety analyses will be performed, unless otherwise specified, using the following common rules:

- Safety data in patients who do not belong to the safety analysis sets (ie, exposed but not randomized) will be listed separately.
- Potentially Clinically Significant Values (PCSVs) or Potentially Clinically Significant Abnormalities (PCSAs) are defined as abnormal values considered medically important by the Sponsor according to predefined criteria/thresholds based on literature review and defined by the Sponsor for clinical laboratory tests, vital signs, ECG (PCSV version dated January 2009 [Appendix 10.4]).

Regeneron Pharmaceuticals, Inc.

Page 42 of 88

Protocol: R4461-PLD-20100

• PCSV criteria will determine which patients had at least 1 PCSV during the respective TEAE period, taking into account all evaluations including unscheduled or repeated evaluations.

Protocol: R4461-PLD-20100

Date: May 16, 2024

- The treatment-emergent PCSV denominator for a given parameter will be based on the number of patients assessed for that given parameter at least once during the respective TEAE period.
- All measurements, scheduled or unscheduled, fasting or not fasting, will be assigned
  to the Global Analysis Windows defined in Appendix 10.2 to provide an assessment
  for the screening visit through follow-up visit time points.
- For quantitative safety parameters including central laboratory measurements and vital sign scores, descriptive statistics will be used to summarize observed values and change from baseline values by visit.
- Unless otherwise specified, in the case of multiple assessments within an analysis
  window, the assessment closest to the protocol planned visit study day will be used in
  analysis.

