#### **5.8.4.** Clinical Laboratory Measurements

General clinical laboratory parameter actual values (quantitative) and change from baseline values will be descriptively summarized at baseline and each post-baseline visit (collected up to the day of last dose of study treatment + 14 days). These parameters will be presented by the biological functions defined in Section 4.8.2.

Individual patient laboratory parameter measurements will be additionally evaluated by PCSV criteria (See Appendix 10.4), specifically identifying patients with at least one post-baseline

Regeneron Pharmaceuticals, Inc.

Page 44 of 88

measurement that meets the PCSV criteria within the respective TEAE period. These laboratory parameters will be presented by the biological functions defined in Section 4.8.2. The incidence of PCSVs at any time during the respective TEAE period will be summarized regardless of the baseline level, and again according to the following baseline categories:

- Normal (according to PCSV criterion/criteria)/missing
- Abnormal according to PCSV criterion or criteria

Patient listings of laboratory measurements that meet PCSV criteria will be provided for the report appendix. For those laboratory parameters that don't have an associated PCSV criteria, similar summary tables can be provided based on measurements outside the central laboratory normal ranges, if applicable.

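### The only joint transaminase-bilirubin row in SAP Table 20 uses ALT alone, so an AST-driven case with raised bilirubin is not counted as joint

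*SAP*

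**What the plan says.** **SAP, Appendix 10.4, Table 20.** ALT and AST each have single-analyte rows at more than 2, 3, 5, 10 and 20 ULN. Total bilirubin has rows at more than 1.5 and 2 ULN. The one combined liver row reads "ALT > 3 ULN and Total Bilirubin > 2 ULN and baseline ALT≤3 ULN or Total bilirubin ≤ 2 ULN".

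**SAP 5.8, General common rules.** The thresholds are the sponsor's own set, cited as "PCSV version dated January 2009 [Appendix 10.4".

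**SAP 5.8.4.** The incidence of these values is tabulated, and "Patient listings of laboratory measurements that meet PCSV criteria will be provided for the report appendix". No other display pairing a transaminase with bilirubin is described. eDISH appears in the SAP's abbreviation list, but the readable text specifies no such analysis.

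**Protocol 8.4.2.1.** Study drug stops for severe liver injury that has no other explanation. With normal baseline enzymes, one criterion is "ALT or AST >3X ULN and total bilirubin >2X ULN", with INR above 1.5 as an alternative to the bilirubin part. With abnormal baseline enzymes the criterion is "ALT or AST >3X over baseline and total bilirubin >2X over baseline (or INR >1.5").

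**Protocol 11.4.5.2.** The number of patients with a potentially clinically significant value (PCSV) "will be summarized for each clinical laboratory test for all patients", that is, test by test.

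**The concern.** A transaminase rise together with a bilirubin rise says more about liver injury than either alone, and the joint row is the only planned display that looks at the two together. The protocol treats ALT and AST as interchangeable in that pairing, and Table 20 treats them alike everywhere except in this row. The SAP gives no reason for leaving AST out.

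At stake is one line of the safety report. In a small study that line may read 0 or 1, and it should not depend on which transaminase rose. A reader who relies on the joint count would have to rebuild an AST-driven case from separate rows or from the listing.

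The row also has a drafting problem: it mixes *and* with *or* and has no brackets.

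**Working it through.** The plan gives no figure to reproduce here. The check sets two logical rules side by side and applies them to illustrative patients. All values are multiples of ULN, baseline → on treatment. The patients are assumptions, not trial data.

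**Rules**
- Current joint row, read as evidently intended: ALT > 3 and bilirubin > 2 and (baseline ALT ≤ 3 or baseline bilirubin ≤ 2).
- Proposed row: the current rule, or the same rule with AST in place of ALT.
- Protocol 8.4.2.1, normal baseline, bilirubin alternative only: (ALT or AST > 3) and bilirubin > 2.
- Single-analyte rows: value > t and baseline ≤ t, for each cut-off t in Table 20.

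| Patient | ALT | AST | Bilirubin | Current row | Proposed row |
|---|---|---|---|---|---|
| 1. AST-driven | 0.8 → 2.8 | 0.8 → 3.5 | 0.6 → 2.2 | 0 | 1 |
| 2. Patient 1 with ALT and AST exchanged | 0.8 → 3.5 | 0.8 → 2.8 | 0.6 → 2.2 | 1 | 1 |
| 3. AST-driven, higher values | 0.8 → 2.5 | 0.8 → 4 | 0.6 → 2.5 | 0 | 1 |
| 4. Raised baseline ALT | 3.2 → 4 | 0.9 → 2.0 | 0.8 → 2.5 | 1 | 1 |

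**Patient 1, step by step**
- Protocol criterion: AST 3.5 > 3 and bilirubin 2.2 > 2, so the numbers are met.
- Current row: ALT 2.8 is not above 3, so 0.
- Proposed row: AST 3.5 > 3, bilirubin 2.2 > 2 and baseline AST 0.8 ≤ 3, so 1.
- Single-analyte rows met: ALT > 2, AST > 2, AST > 3, bilirubin > 1.5 and bilirubin > 2, which is five rows.

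Patient 2 also meets five single-analyte rows (ALT > 2, ALT > 3, AST > 2 and the two bilirubin rows), yet is counted as joint.

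**No case flagged now is lost.** The ALT branch of the proposed row is the current row unchanged, and the AST branch can only add cases. The bilirubin part of the baseline clause has to stay. Patient 4 has baseline ALT 3.2, above 3, and is flagged only because baseline bilirubin 0.8 ≤ 2. Without that part the patient would score 0.

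**Why brackets are needed.** If *and* is evaluated before *or*, as programming languages usually do, the row as printed becomes (ALT > 3 and bilirubin > 2 and baseline ALT ≤ 3) or (baseline bilirubin ≤ 2). A patient with ALT 0.8 → 0.8 and bilirubin 0.6 → 0.6 would then be flagged. A programmer would probably infer the intended meaning, but the SAP should state it.

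**The case against.** The strongest reply is that nothing in the documents requires this row to include AST. PCSVs are sponsor thresholds, and neither document says that they implement the stopping rule. The protocol asks for them test by test, so the joint row already goes beyond what it requires. Patient 1 meets five single-analyte rows, and the qualifying measurements are listed by patient. If the abnormality stops treatment, protocol 10.1.1 says such results "should be reported as AEs if they are symptomatic, lead to study drug discontinuation", and the event then reaches the SAP 5.8.1 table of adverse events leading to permanent discontinuation. SAP 1.2.4 adds the small size of the study: "Due to the early termination of the study and subsequent limited number of participants enrolled". Reading the listings patient by patient is therefore practical.

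Nearly all of this stands, and it is why the point is modest. Two parts do not fully answer it. The adverse-event route is incomplete: the stopping rule applies only where no other cause is found, so a patient who meets the numbers but is given another explanation need not stop and may not appear in the discontinuation table. The reduction to descriptive summaries in SAP 1.2.4 is listed under efficacy analyses, and the safety summaries of SAP 5.8.4, including this row, remain specified. A row that will be produced should not separate two enzymes that the same table otherwise treats alike.

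**Conclusion.** The point holds as a modest reporting improvement. Cases with AST > 3 ULN, ALT ≤ 3 ULN and bilirubin > 2 ULN are missing from the only joint count, though they remain visible in separate rows and listings. No frequency is claimed, because the documents give no liver test data. The conclusion assumes that the baseline clause is read as bracketed above. It concerns only the pairing with bilirubin, not the INR alternative or the protocol's transaminase-only criteria (more than 8 times ULN, or more than 5 times ULN on consecutive visits).

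Three stronger readings are tempting, and the documents do not support them.

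- *The SAP contradicts the protocol, or the stopping rule fails.* The rule operates at the site under protocol 8.4.2.1 whatever Table 20 tabulates, and the SAP does not present the row as that rule.
- *The row should also use multiples of baseline.* Table 20 works in ULN multiples for transaminases and bilirubin and need not mirror the abnormal-baseline branch. The protocol does not say which enzyme makes a baseline abnormal. Such a criterion would also flag normal bilirubin: ALT 1.2 → 3.7 (3.7/1.2 = 3.08) with bilirubin 0.3 → 0.7 (0.7/0.3 = 2.33) would qualify. Equally, the proposed row should not be taken as a count of stopping-rule cases. If either enzyme above ULN makes a baseline abnormal, then AST 1.3 → 1.5, ALT 0.8 → 2.6 (3.25 times) and bilirubin 0.9 → 2.2 (2.44 times) meets the protocol's numbers but neither version of the row.
- *The baseline clause removes patients whose ALT and bilirubin were both already high.* This is unsettled, because SAP 5.8.4 also summarises these values irrespective of baseline and within an abnormal-baseline category.

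**What to change.** In SAP Table 20, replace the joint row with:

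*(ALT or AST > 3 ULN) and total bilirubin > 2 ULN, and (baseline of that transaminase ≤ 3 ULN or baseline total bilirubin ≤ 2 ULN)*

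Keep the brackets as shown and rename the row to cover both enzymes. This is one edited row, programmed from ALT, AST and bilirubin that are already collected. The cost is slightly more output and some AST-driven flags with a non-hepatic cause, which clinical review of the listed patients would have to sort out.

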7.2.2. Exclusion Criteria

A patient who meets any of the following criteria will be excluded from the study:

- 1. Treatment with metreleptin within 3 months of the screening visit
- 2. Patients with a diagnosis of generalized lipodystrophy
- 3. Patients with a diagnosis of acquired lipodystrophy
- 4. Patients with a medical history of bone marrow transplant, use of an immune check-point inhibitor, or central nervous system tumor involving the hypothalamus.
- 5. Patients with clinically significant hematologic abnormalities such as neutropenia, lymphopenia, or lymphadenopathy at screening
- 6. Treatment with over-the-counter or prescription medications for weight loss begun within 3 months prior to the screening visit
- 7. Treatment with oral glucocorticoids >7.5 mg prednisone equivalents per day or plans to begin treatment with oral glucocorticoids >7.5 mg prednisone equivalents per day during the study period
- 8. Treatment with oral estrogens begun within 6 months prior to the screening visit
- 9. Any malignancy, eg, lymphoma, within the past 1 year, prior to screening visit except for fully treated basal cell or squamous epithelial cell carcinomas of the skin or carcinoma in situ of the cervix or anus
- 10. Estimated glomerular filtration rate (GFR) of <30 mL/min/1.73 m² based on the Chronic Kidney Disease Epidemiology Collaboration (CKD-Epi) equation at screening
- 11. History of heart failure hospitalization, myocardial infarction, stroke, clinically-significant arrhythmia (eg, ventricular tachycardia, or any arrhythmia requiring medication adjustment

- to control), transient ischemic attack, unstable angina, percutaneous or surgical revascularization procedure (coronary, carotid, or peripheral vascular), or intracardiac device placement (eg. pacemaker) within 3 months before the screening visit
- 12. Advanced heart failure (New York Heart Association Class 3 to 4) or severe and uncontrolled hypertension at screening
- 13. Current diagnosis of Type 1 diabetes mellitus
- 14. History of human immunodeficiency virus (HIV) or HIV seropositivity at screening visit
- 15. Uncontrolled infection with hepatitis B or hepatitis C infection or known active tuberculosis at screening.

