#### Clinical chemistry:

- Electrolytes: sodium, potassium, chloride, carbon dioxide, calcium
- Metabolism: fasting glucose, total protein, albumin, Creatine phosphokinase
- Renal function: creatinine, blood urea nitrogen (BUN), uric acid
- Liver function: Alanine aminotransferase (ALT), aspartate aminotransferases (AST), alkaline phosphatase (ALP), total bilirubin, LDH, Gamma-glutamyl transferase (GGT)

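### The creatinine-clearance PCSV row in SAP Table 20 has its worst band closed at 15, so a value below 15 falls in no class on that row

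*SAP*

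**What the plan says.** SAP Appendix 10.4, Table 20, gives creatinine clearance three bands, each closed at both ends. The worst is "≥15 - <30 (severe decrease in GFR" and the other two are "≥30 - <60 (moderate decrease in GFR) ≥60 - <90 (mild decrease in GFR". The row states no unit, no equation and no baseline condition. The serum creatinine row just above it has two thresholds, "≥ 30% increase from baseline ≥ 60% increase from baseline", with no upper limit. Blood urea nitrogen has its own row, at 17 mmol/L or more.

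On counting, the general common rules of SAP 5.8 say that "PCSV criteria will determine which patients had at least 1 PCSV during the respective TEAE period", and they bring in unscheduled and repeat evaluations. SAP 5.8.4 applies the table to laboratory data: "Individual patient laboratory parameter measurements will be additionally evaluated by PCSV criteria". It lists the measurements that meet a criterion. It reserves summaries against the laboratory normal range for parameters that have no PCSV criterion.

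The renal variables in SAP 4.8.2 are given as "Renal function: creatinine, blood urea nitrogen (BUN), uric acid". Neither creatinine clearance nor eGFR appears there, or in the laboratory tests of protocol 9.2.4. The only renal-function estimate in the protocol is exclusion 10 (section 7.2.2): "Estimated glomerular filtration rate (GFR) of <30 mL/min/1.73 m² based on the Chronic Kidney Disease Epidemiology Collaboration (CKD-Epi) equation at screening".

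**The concern.** In a graded abnormality row, the worst tier should catch everything beyond its threshold. Here milder values are flagged and the most extreme are not. The other tiered laboratory rows in Table 20 do not work this way. ALT and AST end at >20 ULN. CPK closes its first two tiers and leaves the last open at >10 ULN. The floor of 15 therefore looks like an omission, not a convention of the table.

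The fallbacks in SAP 5.8.4 do not repair the row. Because it has a criterion, the normal-range summary does not apply. Because only values meeting a criterion are listed, a value below 15 is missing from this row's listing as well as its count.

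What is at stake is the severity class shown for a renal event. The protocol's introduction notes nephropathy risk in partial lipodystrophy patients with diabetes. Enrolment was small, so one misclassified patient is visible in the table. The early-termination changes in SAP 1.2.4 cut back the efficacy analyses and drop the step analyses, but leave the PCSV summaries in place.

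**Working it through.** The plan states no figure to reproduce here. The check is of a threshold table.

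**1. Which values meet a band.** Inputs: the three bands in SAP Table 20.

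| Value | Class on the row |
|---|---|
| 5, 10, 14.9 | none |
| 15, 29.9 | severe |
| 30, 59.9 | moderate |
| 60, 89.9 | mild |
| 90 | none |

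Below 90, the uncovered values are exactly those below 15.

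**2. What this does to a patient on the row.** A PCSV counts any evaluation in the TEAE period, so three cases arise for a patient whose worst value is below 15:

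- Another value in the period lies in 15 to <30. The patient is counted as severe, but the value below 15 is not in the row's listing.
- No value lies in 15 to <30, but one lies in 30 to <90. The patient is counted only as moderate or mild.
- No value lies in 15 to <90. The patient is not counted on this row at all.

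**3. Whether the creatinine row catches the same patient.** The documents give no relation between creatinine and clearance, so two assumptions set a range:

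- (a) Clearance inversely proportional to creatinine: rise = B/15 − 1, where B is baseline renal function.
- (b) GFR proportional to creatinine to the power −1.2: rise = (B/15)^(1/1.2) − 1.

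The starting point of 30 is the entry floor in exclusion 10.

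| Baseline B | Rise under (a) | Rise under (b) |
|---|---|---|
| 30 | 30/15 − 1 = 100% | 2^(1/1.2) − 1 = 78% |
| 45 | 45/15 − 1 = 200% | 3^(1/1.2) − 1 = 150% |
| 60 | 60/15 − 1 = 300% | 4^(1/1.2) − 1 = 218% |
| 90 | 90/15 − 1 = 500% | 6^(1/1.2) − 1 = 345% |

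All exceed the 60% criterion. Conversely, the lowest baseline from which a fall to 15 means a 60% rise is 15 × 1.6 = 24 under (a) and 15 × 1.6^1.2 = 26.4 under (b). Both lie below 30.

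One limit applies. The floor of 30 is a CKD-EPI value at screening, while the row's measure is undefined. A baseline below about 24 to 26 on the row's own scale is therefore unlikely but not strictly excluded. That is why the conclusion is very likely rather than certain.

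**4. After the fix.** With an added class for values below 15, the bands cover every value below 90 without a gap.

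**The case against.** The strongest objection is to the text itself. Table 20 is known here only as machine-read text, and its triglycerides row is visibly damaged. A <15 line would begin with the character most likely to be lost. Against that, other entries beginning with the same sign survive in the table (chloride <80, potassium <3, lymphocytes <0.6). Loss is possible but not shown. The objection stands as a reason to check the source document before editing, not as a reason to drop the point.

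Second, detection does not rest on this row. The creatinine and BUN rows remain, and SAP 5.8.4 gives by-visit creatinine summaries. Protocol 9.2.4 requires significantly abnormal results to be repeated. A repeat or unscheduled value in 15 to <30 would put the patient in the severe class. This stands, and it limits the effect to the class and listing on one row.

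Third, the row may be little used. SAP 5.8.4 presents parameters by the functions in 4.8.2, which omits clearance, and the criteria list is a sponsor version dated January 2009. This also stands: the documents do not support calling the row a main renal safety output.

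Two stronger readings are tempting, and neither is supported.

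- A reader might infer that the row contradicts the protocol by replacing CKD-EPI eGFR with another measure. Exclusion 10 uses that estimate only for eligibility at screening, and nothing commits the safety analysis to it. The row itself labels its bands as decreases in GFR. What is missing is a definition.
- A reader might infer that weight loss on drug would move patients into worse bands and so bias the row against REGN4461. That needs a weight-proportional formula, and the documents state none.

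**Conclusion.** Wrong as written, minor. Followed literally, the row assigns no class to values below 15 while flagging 15 to <90. The consequence is a wrong severity-class count and an incomplete listing on this row. It is not an undetected patient: from a baseline of 30 or more, a fall below 15 implies a creatinine rise of at least about 78%, which meets the separate 60% criterion.

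This rests on three things: the extracted table being complete, the two assumed creatinine relations, and the entry floor of 30 being a fair guide to baseline on the row's undefined scale. The documents give no basis for estimating how often such a value would occur, and no conclusion of the trial is shown to change. The missing unit and equation are a secondary weakness, because two programmers could derive different counts from the row as it stands.

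**What to change.** 1. Check the source document for a <15 line on the creatinine-clearance row. If it is there, the main point falls away and only step 3 remains.
2. If it is not, add an open-ended <15 class as the worst tier of that row.
3. State the unit and equation for the row and add the variable to the renal list in SAP 4.8.2. CKD-EPI eGFR in mL/min/1.73 m² is a convenient choice because exclusion 10 already uses it, but the documents do not require it.

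The cost is SAP wording and one derived variable from creatinine already collected, with no new data. The SAP overview allows revision before the final database lock. The severity count could become slightly less favourable if such a value occurred.
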